#### **Effects of the Covid19 pandemic:**

- Due to the outbreak of the Covid19 Pandemic, the ILCOR and the Swedish Resuscitation Council issued temporary guidelines for lay bystander CPR in OHCA, recommending only looking for signs of life and performing chest compressions only.(26, 27) Therefore, this study was put on hold on date: 12-03-2020.
- The initial plan was to publish the Pilot-study including years 2017 and 2018. Due to the uncertainty during the Covid19-pandemic regarding whether the trial would be able to restart a decision by the steering committee was made to postpone the pilot publication.
- During the pause due to the Covid19-pandemic an independent data monitoring committee reviewed all data up until 12-03-2020 (pre-Covid19). Their recommendation was to continue the trial without modifications, please see also "11. Interim analysis and data monitoring committee".
- When the temporary Covid-19 guidelines were removed the 1 April 2022 the main trial was relaunched, and inclusion started in August 2022.
- A decision was made to include all patients during the period pre-Covid19 in the Pilot-study and the dates of the pilot-study were changed accordingly.
- To assure follow-up all, all EMS records of all calls of suspected OHCA with no matching record in SCAR will be reviewed. Please see "8. Data Collection"

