## 10. Data analytic and statistical analysis plan (SAP)

### 10.1 General statistical analysis plan

This trial is designed to investigate whether CO-CPR is no worse than S-CPR using a non-inferiority design. It has also been designed for the possible of a superiority testing. This statistical design has been chosen appropriately judged on the presumption that CO-CPR has potential clinical benefit but also is easier to perform (and therefore would lead to a higher number of patients receiving the treatment). The largest difference in 30-day survival (primary outcome) that is considered clinically relevant is 1.0 percentage point (please see also section 9.3).

Eligibility, allocation, inclusion and exclusion will be displayed in a Consort diagram. Differences in proportions between baseline characteristics and outcome will be tested by Fisher exact test. Differences in mean or medians between the treatment groups will be tested by either Student's t-test or Mann Whitney U test depending on distribution. Normality assumptions will be assessed with Kolmogorov Smirnov – test. The estimated between group differences will be presented as proportions and 95% confidence intervals (CI), which will be calculated by the asymptotic method without continuity correction. P-values below 0,05 will be considered statistically significant. Main results will be reported as proportions.

In addition, comparisons between the treatment groups (CO-CPR vs CPR) with respect to the outcomes will be adjusted for background characteristics factors through Binary logistic regression to adjust for possible imbalances due to randomization between the treatment groups. The association between treatment and primary outcome will be presented as odds ratios and corresponding 95% CI intervals. Statisticians at Karolinska Institutet will be responsible for the statistical analysis.

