## 10.5 Power and sample size estimation

We estimated that 3260 patients (1630 in each group) would be needed in the primary analysis PP1 to have 80% power to show that CO-CPR is non-inferior to standard CPR. This calculation is based on the assumptions that the true survival rates after 30 days (primary outcome) in the population for standard CPR is 11% compared with 13.1% for CO-CPR, and that alpha (1 tailed) is set at 2.5%.

We defined 1.0 percentage point or less as the largest difference in survival that is clinically acceptable (i.e. the non-inferiority level which imply that a difference bigger than this would matter in practise). This difference is equivalent to an NNT of 100 (one person of 100 will die among those recommended CO-CPR, due to this recommendation). The reason for accepting this difference relies on the assumption that CO-CPR is easier to teach and perform, and therefore the treatment can be offered to more victims (please see also section 9.3).

In addition, we assumed that 20% will not receive the allocated intervention (e.g. randomized to CO-CPR but received S-CPR instructions or vice versa). We also assumed that 40% of the included patients will be excluded because of exclusion criteria's not possible to detect at the randomization (not OHCA, see section 5.3). Therefore, the recruitment goal was set to 6792 ( $3260 / (0.8 * 0.6)$ ) randomized cases of suspected out-of-hospital cardiac arrest in order to receive 3260 in the primary PP1 analysis. (Please see also Consort Flow Diagram below)

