## **10.7 Subgroup analyses**

Subgroup analyses will be performed for the primary outcome variable using logistic regression models with test of treatment-subgroup interaction for each of the predefined subgroup variables. The results will be presented as the odds ratio with 95 % confidence interval for each subgroup and the corresponding p-value for interaction between treatment and each subgroup variable.

Subgroups will be analyzed according to the following pre-defined variables:

- Gender
- Age
- Cause of OHCA
- Initial rhythm
- Place of cardiac arrest
- Time to start of CPR
- Time to arrival of EMS
- Neurological severity classification (CPC)

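### The primary PP1 analysis pools patients from before and after the roughly 29-month Covid pause without a period term, so arm-specific drift in dispatcher adherence, if survival also changed between periods, would bias the crude difference

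*Combined protocol and SAP*

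**What the plan says.** **Two recruitment periods, one analysis.** Sections 7.1 and 7.2 carry pilot patients into the main survival analysis, and section 7.3 extends the pilot to everyone recruited before Covid. The trial was put on hold on 12-03-2020 (read here as 12 March 2020) because temporary guidelines for lay rescuers were issued, "recommending only looking for signs of life and performing chest compressions only". On the restart, section 7.3 says: "When the temporary Covid-19 guidelines were removed the 1 April 2022 the main trial was relaunched, and inclusion started in August 2022".

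**How the primary set is formed.** Section 10.6 runs the primary non-inferiority test in PP1, then repeats it in ITT and PP2. Section 10.4 defines PP1 as ITT patients whose bystanders were given the allocated instruction by the dispatcher, as judged by call audit. Section 10.5 assumes one non-adherence figure, 20%, for both arms and all periods.

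**How the difference is estimated.** Section 10.1 plans a difference in proportions with an asymptotic 95% CI: "Main results will be reported as proportions". An additional logistic regression adjusts for baseline factors that are not listed. Section 10.7 states "Subgroups will be analyzed according to the following pre-defined variables" and gives eight variables. Calendar period is not among them, and it is not named as a covariate anywhere.

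**The concern.** Allocation is concurrent and 1:1, so in each period the randomised arms are comparable. That protection does not pass to PP1, because membership depends on what the dispatcher did after allocation. For about two years of the pause the recommended form of lay CPR was the trial's intervention. If some of that habit persisted among dispatchers, S-CPR allocations could be followed less often after restart than CO-CPR allocations. The S-CPR arm of PP1 would then hold relatively fewer late patients than the CO-CPR arm. If 30-day survival also changed between the two periods, part of that change would appear as a treatment difference.

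At stake is an estimate judged against a 1.0-point margin. Readers will also ask whether the effect was the same before and after the pause, and the plan pre-specifies no analysis that answers this.

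**Working it through.** **1. The plan's own sample size.** Section 10.5 gives 1630 per arm for "80% power to show that CO-CPR is non-inferior to standard CPR", with survival "in the population for standard CPR is 11% compared with 13.1% for CO-CPR" and "alpha (1 tailed) is set at 2.5"%. On the margin it says: "We defined 1.0 percentage point or less as the largest difference in survival that is clinically acceptable". The standard unpooled formula is

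n = (1.960 + 0.842)² × (0.11×0.89 + 0.131×0.869) / (0.021 + 0.010)² = 1730 per arm,

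and power at 1630 is 77.6%. The stated figure is therefore not reproduced exactly. Less usual variants come close: control-arm variance in both arms gives 1599, and a CO-CPR rate of 13.2% gives 1629. The recruitment goal does reproduce: 3260/(0.8×0.6) = 6792. The present point does not depend on this, and 3260 is taken as given. The planned 95% CI half-width at 1630 per arm is about 2.2 points.

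**2. Dates.** From 12 March 2020 to August 2022 is 28.6 to 29.6 months. From the hold to the lifting of the guidelines on 1 April 2022 is 24.6 months, so roughly the last four months of the pause came after the advice had ended. The start date of the guidelines is not given.

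**3. Pre-pause share of PP1.** Section 11 reports 696 PP1 patients at the early-2022 review, and section 7.3 says that review covered all data up to the hold. 696/3260 = 21.3%, leaving 2564 to be recruited afterwards.

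**4. Bias through period mix.** These inputs are assumptions, not figures from the documents: the 696 split equally (348 per arm), post-restart retention r by arm, a survival change d between periods, the same treatment effect in both periods, and adherers comparable with non-adherers.

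- Post-restart PP1 patients in an arm: 2564 × r / (r_S + r_CO)
- Post-restart share w = that number / (348 + that number)
- Bias = (w_CO − w_S) × d

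For 70/90%, S-CPR has 1121.8 late patients of 1469.8, and CO-CPR has 1442.2 of 1790.2.

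| Retention S-CPR / CO-CPR | w_S | w_CO | Difference (unrounded shares) | Bias, d = 1 point | Bias, d = 3 points |
|---|---|---|---|---|---|
| 80 / 80% | 78.65% | 78.65% | 0 | 0 | 0 |
| 75 / 85% | 77.55% | 79.65% | 2.10 points | 0.02 | 0.06 |
| 70 / 90% | 76.32% | 80.56% | 4.24 points | 0.04 | 0.13 |
| 60 / 90% | 74.67% | 81.55% | 6.89 points | 0.07 | 0.21 |

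If survival falls after restart, the sign reverses. If d = 0, every row is zero.

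**5. Error rate at the margin.** Type I error = Φ(bias/SE − 1.96). At 70/90%, SE is about 1.08 points. With d = 2 the error is 0.030 and with d = 3 it is 0.033, against 0.025. With d = −3 it is 0.019.

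**6. Precision cost of stratifying.** At 70/90% and 11% survival throughout:

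- Crude SE = √[0.0979 × (1/1790.2 + 1/1469.8)] = 1.101 points.
- Mantel-Haenszel SE = √[0.0979 / (174 + 631)] = 1.103 points, where 174 and 631 are n_CO × n_S/(n_CO + n_S) in each period.

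Under the assumptions in step 4 the stratified difference has no bias from period mix.

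**7. What stratifying leaves.** Suppose post-restart retention is 90% (CO-CPR) and 70% (S-CPR), and adherers survive 2 to 5 points more than non-adherers. Selection within that period then contributes (0.10 − 0.30) × 2 to 5 = −0.4 to −1.0 points, against CO-CPR. It reverses if non-adherers do better. A period term removes none of this.

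**The case against.** The case against is substantial.

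- **Two conditions are needed.** A reader might infer that any arm-specific drift after restart confounds the result. It does not: drift without a survival change gives zero bias through period. The documents report neither retention by arm and period nor survival by period, so every size above is hypothetical.
- **Only the dispatcher's instruction counts.** A reader might infer that callers who leave out breaths drop out of the S-CPR arm. Section 10.4 defines PP1 by the instruction given, so they stay in. That may dilute the contrast, but it is not confounding by period. Dispatchers also see on-screen instructions for the allocated arm (section 6.2.1), and call auditors are blinded to allocation (section 8), which limits the scope for drift.
- **The advice did not span the whole pause.** It was lifted about four months before inclusion restarted, and the documents do not say that bystanders were trained in compressions only.
- **Larger biases need a larger pre-pause share.** The reported 696 fixes that share at about 21% unless PP1 ends well short of 3260.
- **Partial safeguards exist.** ITT is analysed in the same way and is not confounded by period. The adjusted logistic model could include period, although its covariates are unnamed.
- **The larger threat lies elsewhere.** Selection within a period can exceed the bias through period mix, and stratification might give false comfort about PP1.

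All of this stands, and it keeps the point modest. It does not remove it. The estimator that decides the trial is crude, it is applied to a set selected after randomisation, and ITT comes second. That the effect by period could be computed later from the collected dates is true, but an unplanned analysis would carry less weight.

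**Conclusion.** The point holds in a limited form. The crude PP1 difference is open to bias from unequal period mix if two things happen together: retention in PP1 drifts differently by arm after restart, and 30-day survival differs between periods. Under assumed retention of 70/90% and a change of 1 to 3 points, the bias is 0.04 to 0.13 points, or 4% to 13% of the margin. At 60/90% it is 0.07 to 0.21 points. That is small beside a CI half-width of about 2.2 points, but it can move the type I error above 2.5% or below it. The documents do not show that such drift occurred, and they do not support reading the pause as a fatal flaw or the ITT result as affected. The change is worth making because it removes this component at almost no cost, not because the component is large.

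**What to change.** 1. In sections 10.1 and 10.6, estimate the PP1 30-day survival difference as a Mantel-Haenszel risk difference stratified by period (randomised up to 12 March 2020, or from August 2022), and compare its 95% CI with −1.0 point. At the least, pre-specify this as a sensitivity analysis beside the crude estimate.
2. Add period to section 10.7 with the interaction test already planned there. It will be imprecise: with 348 and 1282 per arm at 11% survival, the SE of the between-period difference in effect is √[2 × 0.0979 × (1/348 + 1/1282)] = 2.7 points. It should be read as descriptive.
3. Report PP1 retention by arm and period in the CONSORT diagram.
4. State in section 10.4 that stratification by period does not remove selection into PP1 within a period, and that PP1 is to be interpreted together with ITT.

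The cost is SAP wording and one stratification factor, fixed before allocation is unblinded for the final analysis. Date of OHCA, time of randomisation and audited instructions are already collected under section 8. No new patients or data are needed, and in the example above the SE rises only from 1.101 to 1.103 points.

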## 8. Data collection

### From the dispatch organization (SOS-Alarm AB) the following variables will be collected:

Time of incoming call, time of dispatch of EMS, time of dispatch of first responders when applicable, time for screening for inclusion, time of randomization and time of arrival of EMS and first responders. Event times are automatically generated and stored in the dispatch organization's computer system. The randomized assignment for each call is stored in a separate data-file generated by the random sequence constructor.

For evaluation of included calls and adherence to protocol all randomized, EMS treated OHCA dispatch calls will be audited. All audit evaluators will be blinded to allocation. A standardized template for evaluation of dispatcher assisted CPR will be used (cardiac arrest registry to enhance survival – CARES).(25) The study specific inclusion criteria will be added as auxiliary variables (supplementary app).

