**The instructions from the dispatcher in INTERVENTION arm include:**

- An ambulance is dispatched and is on its way to you
- Do CPR with chest compressions only
- Push hard on the chest with a pace of 100/minute without interruptions for rescue breathing.

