**The Instructions from the dispatcher in the CONTROL arm include:**

- An ambulance is dispatched and is on its way to you
- Do CPR with chest compressions and rescue breathing
- Push hard on the chest 30 times and give 2 rescue breaths. The pace of the compressions should be 100/minute.

Dispatchers are furthermore instructed to encourage all callers in both groups to stay in connection with the callers until arrival of EMS or first responders, instruct callers to put the phone on loudspeaker when possible and to ask callers to count aloud while performing chest compressions. Dispatchers should try to aim for a compression rate of 100-120/minute and suggest switching CPR-provider every 2 minutes if multiple rescuers are on the scene.

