### **7.3 Summary of changes in protocol after experiences from the pre study RUN-IN period and effects of the Covid19 pandemic.**

**Previous changes from original protocol (February 2019):**

- As described above, the start and size of the PILOT-study was modified to include all patients during 2 years (2017-18).
- As a consequence of the national expansion, enlargement of the PILOT study as well as the seamless design, the primary endpoints of the PILOT study was modified not only to asses feasibility but also to include assessment of safety as well as intermediate clinical outcomes until hospital admission.
- The initial secondary endpoint of 30-day survival is not evaluated in the PILOT study. The reason for this is to not interfere with the primary endpoint of the MAIN study.
- Inclusion / Exclusion criteria and intervention/control instructions have remained unchanged since the first initial protocol throughout all parts of the TANGO2 project.
- In Stockholm, first responders are dispatched in parallel to EMS in suspected OHCA. The initial protocol included first responders as a part of the trial. However, due to the national expansion of the study together with the fact that the information of assigned treatment (CO-CPR or S-CPR) to first

responders during dispatch in the RUN-IN phase was not feasible, the steering committee decided to remove first responders from participation in the PILOT study and the MAIN study.

- The initial protocol stated a randomization procedure through the opening of pre-printed envelopes with randomized allocation. This was changed before the start of the pre study RUN-IN period to an automated computerized randomization integrated in the dispatchers' software.
- For assessment of adherence to protocol a decision was made by the Steering Committee to audit all calls during the PILOT study and MAIN study using a standardized template for evaluation of dispatcher assisted CPR (cardiac arrest registry to enhance survival – CARES)(25) and that all audit evaluators will be blinded to allocation.

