## 10.4 Analysis step and strategy of the whole study populations

The target study population is witnessed OHCA of medical origin where any bystander at the scene has previous CPR training. All randomized calls of suspected OHCA will be included.

Patient with previous decision that CPR should not be initiated i.e. terminal illness or palliative care and cases where EMS did not start CPR for other reasons (sure signs of death, not true OHCA) will be excluded from data analysis. The remaining patients will be analyzed in the ITT population.

Blinded call audit will be used to define type of CPR instructions provided. All randomized EMS treated OHCA receiving instructions in accordance with randomized allocation will be treated as the target study population treated per protocol (PP1).

Finally, patients who are randomized but later judged as not fulfilling all criteria for inclusion before randomization, as evaluated by call audit (not witnessed, asphyxic, bystanders with no previous CPR training), will be removed and remaining patients will be analyzed as PP2.

Thus, we perform ITT analysis, PP1 and PP2 analysis based on the following patients:

Intention to treat (ITT) analysis: We define the ITT population as all included and randomized EMS treated OHCA patients that not fulfilled any exclusion criteria's.

Per protocol 1 (PP1): We define the PP population as the subset of the ITT population where the bystanders received the allocated instructions by the dispatch operator, as defined by the call audit.

Per protocol 2 (PP2): We define the PP2 population as the subset of the PP1 population where the patients fulfilled all inclusion criteria, as defined by call audit.

Please see also Consort Diagram in section 10.5.

The reasoning behind excluding patients after randomization is two-folded:

First: Dispatchers suspecting OHCA based on initial information in a phone-call do patient inclusion and randomization. In this situation there is very limited information and dispatchers are encouraged to treat all calls where the patients are not conscious and not breathing normally as suspected OHCA

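### Audit evaluators are blinded to the allocation file, but not to the arm, when they make the eligibility judgements that define PP2

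*Combined protocol and SAP*

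**What the plan says.** Section 7.3 introduces an audit of all calls and says "all audit evaluators will be blinded to allocation". Section 8 repeats this for the audit of randomised, EMS-treated calls: "All audit evaluators will be blinded to allocation". The mechanism described is administrative. In section 8, "The randomized assignment for each call is stored in a separate data-file generated by the random sequence constructor", and section 8.1 keeps allocation blinded in the study database during data collection.

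The audit has two tasks under section 10.4:

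- **Instruction rating (PP1).** "Blinded call audit will be used to define type of CPR instructions provided". PP1 follows from it: "We define the PP population as the subset of the ITT population where the bystanders received the allocated instructions by the dispatch operator".
- **Eligibility rating (PP2).** PP2 is PP1 without the patients "later judged as not fulfilling all criteria for inclusion before randomization, as evaluated by call audit". The items listed are an unwitnessed collapse, asphyxia, and bystanders without CPR training. Section 8 adds the inclusion criteria to the same audit template as auxiliary variables.

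Section 10.6 makes PP1 the primary analysis. It then applies the same non-inferiority and superiority sequence to ITT and PP2, with a 1% limit.

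**The concern.** An auditor cannot classify the instruction without hearing it, and the two scripts in section 6.2.1 name the technique openly: "Do CPR with chest compressions only" or "Do CPR with chest compressions and rescue breathing". Withholding a file therefore does not hide the arm from the person who also decides eligibility.

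Whether a collapse was witnessed, whether the cause was asphyxia and whether a bystander was trained are matters of judgement. They are judged from calls that section 10.4 itself describes as giving very little information. If knowledge of the arm affects how borderline calls are read, patients with a poor prognosis could be removed from one arm more often than from the other. That would shift the PP2 survival difference in either direction. A report could then describe PP2 as selected by blinded audit when the written procedure does not ensure it.

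**Working it through.** The plan gives no figure for this point, so there is none to reproduce. The first part is logic from the definitions. The second is a sensitivity calculation.

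**1. When the arm is audible**

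- PP1 contains only calls in which the instruction heard equals the allocation (10.4). Within PP1 the instruction reveals the arm in 100% of calls, by definition.
- PP2 is formed only by removing calls from PP1 (10.4). Every call at risk of removal is therefore one in which the allocated arm was audible.
- Across all audited calls, section 10.5 assumes that 20% do not receive the allocated intervention. The instruction heard then matches the allocation in about 1 − 0.20 = 80%. While scoring, the auditor does not know which calls will fall in PP1, so 80% describes how reliable the inference is from the auditor's side.
- The available text gives no separate eligibility reviewer, no cut in the recording, and no rule that eligibility is scored before the instruction is heard.

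**2. How much uneven removal would matter**

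Inputs from section 10.5: 1630 per arm in PP1, 11% survival with standard CPR, margin 1.0 percentage point. Expected survivors per arm: 0.11 × 1630 = 179.3.

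If x extra non-survivors are removed from one arm only, survival in that arm becomes 179.3 / (1630 − x).

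| Extra non-survivors removed | Survival in that arm | Shift (points) |
|---|---|---|
| 36 | 179.3/1594 = 11.25% | 0.25 |
| 40 | 179.3/1590 = 11.28% | 0.28 |
| 48 | 179.3/1582 = 11.33% | 0.33 |
| 136 | 179.3/1494 = 12.00% | 1.0 |

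If 5% of those removed are survivors (an assumption), a shift of 1.0 point requires (179.3 − 0.05x)/(1630 − x) = 0.12. This gives x = 16.3/0.07, or about 233.

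**3. A range under stated assumptions**

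The documents give neither the share of PP1 that is truly ineligible nor the survival of those patients. Assume 11% survival overall in both arms, a truly ineligible share q with survival s, and removal of all ineligible patients in one arm but only half in the other. Survival among the eligible is h = (0.11 − q·s)/(1 − q). The shift is h − [(1 − q)h + 0.5·q·s]/(1 − 0.5·q).

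| q | Shift with s = 6% | Shift with s = 0% |
|---|---|---|
| 5% | 0.13 | 0.30 |
| 10% | 0.29 | 0.64 |
| 20% | 0.69 | 1.53 |

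For q = 10% and s = 0: 0.11/0.90 − 0.11/0.95 = 12.22% − 11.58% = 0.64 points. That row implies an excess removal of 0.5 × 0.10 × 1630, or about 82 patients in one arm. With equal removal in both arms the shift is zero.

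**The case against.** Much of the case on the other side stands.

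- **The blinding sentence can be literally true.** Auditors do not see the allocation file, so they rate the instruction without knowing whether it matches. That is the protection PP1 needs. In section 10.4 the word blinded is attached to the instruction rating, not to the PP2 removals. A reader might infer that the audit blinding fails altogether or that PP1 is compromised; the documents do not support that.
- **PP2 is secondary.** Section 10.4 gives the target-population label to PP1, calls the PP2 analysis secondary, and warns that removing further patients might interfere with real-life interpretation. Neither PP1 nor ITT uses the audit's eligibility judgement.
- **The margin is not a count of removals.** A reader might note that 1.0 point of 1630 is about 16 patients and infer that a few dozen uneven removals would use up the margin. The 16 are survivors. Removing non-survivors only shrinks the denominator, and section 2 of the working shows that about 136 are needed.
- **Outcome knowledge is not shown.** A reader might infer that auditors know survival because calls are audited after EMS attendance. EMS-treated status does not reveal 30-day survival, and no section gives auditors survival data.
- **The audit appendix is unseen.** Section 8 refers to supplementary material for the added eligibility variables. It may set a scoring order or a masking step.

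What remains is that the main text makes a general blinding claim, and the procedure it describes does not deliver that claim for the eligibility judgements.

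**Conclusion.** The point holds in limited form. Blinding to the allocation file protects the PP1 rating. The PP2 eligibility judgements are made with the allocated arm audible in every call that can be removed, and no safeguard appears in the available text. The primary conclusion is not affected; the exposure is in the secondary PP2 non-inferiority and superiority tests.

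The likely size is modest. A one-sided excess of 40 non-survivors moves an arm by about 0.28 points against a 1.0-point margin. Among the scenarios in which half the ineligible patients are kept in one arm, only those with 20% ineligible can exceed 1.0 point. These sizes rest on 11% survival, 1630 per arm, and assumed ineligible shares and survival that the documents do not give. The direction is unknown, and nothing shows that uneven removal has occurred. The change is still worth making because it is cheap and makes the blinding statement accurate.

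**What to change.** In sections 8 and 10.4:

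1. **Order the audit template.** Score and lock the eligibility items on the recording up to the stored time of randomisation. Only then play and classify the instruction. This fits the plan: section 10.4 defines PP2 by criteria before randomisation, section 8 collects the time of randomisation, and section 8.1 keeps the audio.
2. **Handle later information separately.** Record eligibility facts that emerge after randomisation as their own variables and use them in a sensitivity version of PP2. Include a code for items not established by the cut-off and say how such calls are treated. Section 6.2.1 lets a call proceed when CPR is already under way, so training may not have been stated by then.
3. **Calls already audited in one pass.** Either re-score eligibility on truncated audio whatever the existing judgement was, or state that their PP2 status was judged with the instruction audible. The re-score can cover all calls, or a random sample of both eligible and ineligible calls as a check. Re-scoring only those judged ineligible or unclear would miss ineligible patients wrongly kept.
4. **Report** PP1-to-PP2 removals by arm and reason.
5. **Limit the blinding claim** to the allocation file and the locked eligibility step.

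The cost is extra work for the existing auditors. Section 11 reports 696 patients in PP1 at the early-2022 review, which indicates the scale of a full re-score of the earlier PP1 calls. The other downside is that late-emerging facts do not count in the main PP2 definition.
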